4 STUDY DESIGN

4.1 Overall Design

This is a randomized, Phase 3, placebo-controlled, multisite, double-blind study of chemoradiotherapy with or without pembrolizumab in participants with high-risk LACC.

Approximately 980 participants will be enrolled in the global portion of the study. After enrollment of the global portion of the study is complete, the study may remain open to enrollment in China alone until the target number of participants in China has been enrolled to meet local regulatory requirements. An extension portion of the study will be identical to the global study, (eg, inclusion and exclusion criteria, study endpoints, primary and secondary objectives, study procedures, and statistical analyses).

Eligible participants with high-risk LACC FIGO 2014 Stage IB2-IIB (with node-positive disease) or Stage III-IVA (either node-positive or node-negative disease) will be randomly assigned in a 1:1 ratio to one of the following treatment arms:

- 1) Concurrent chemoradiotherapy in combination with pembrolizumab (200 mg Q3W for 5 infusions) followed by pembrolizumab alone (400 mg Q6W for 15 infusions) or
- 2) Concurrent chemoradiotherapy in combination with placebo (Q3W for 5 infusions) followed by placebo alone (Q6W for 15 infusions).

Standard of care CCRT is given during the Q3W dosing period of pembrolizumab (Arm 1) or placebo (Arm 2) and includes the following:

- 1) Cisplatin, 5 infusions given IV QW at 40 mg/m² (an optional, sixth infusion of cisplatin may be administered according to local practice) plus

- 2) EBRT over 40 days, followed by
- 3) Brachytherapy

Note: brachytherapy should follow the completion of EBRT, and the overall treatment time of EBRT and brachytherapy together should not exceed 50 days (with an extension to a maximum of 56 days for unforeseen delays). The minimum acceptable radiation is 80 Gy for volume-directed and 75 Gy for point-directed. Please refer to the Radiation Manual for further guidance.

Geographic variance in total radiation dose administered, number of fractions and methodology of application may be permitted after consultation with the Sponsor.

The SOC will be at least 3D conformal planning.

To limit overall treatment time, efficient organization of the whole multimodal treatment is required. This includes use of SIB in participants with lymph node involvement, minimizing treatment interruptions as much as possible and by planning the timing of brachytherapy carefully.

Specific procedures to be performed during the study, as well as their prescribed times and associated visit windows, are outlined in the SoA in Section 1.3 ([Table 1](#)). Details of each procedure are provided in Section 8.

There will be 2 formal interim analyses. The first interim analysis will be conducted when approximately 237 PFS events are observed. The second interim analysis will be conducted when approximately 304 PFS events are observed. A final analysis will be conducted when approximately 240 OS events are observed.

Results of the interim and final analyses will be reviewed by the external DMC, who will make recommendations to the Sponsor to continue, modify, or end the study according to the plan described in Section 9.

4.2 Scientific Rationale for Study Design

MK-3475 A18/ENGOT-CX11/GOG3047 is a randomized, Phase 3, double-blind study of chemoradiotherapy with or without pembrolizumab for the treatment of high-risk, locally advanced cervical cancer.

The purpose of this study is to evaluate the efficacy and safety of pembrolizumab plus concurrent chemoradiotherapy compared with placebo plus concurrent chemoradiotherapy in participants with locally advanced cervical cancer.

The primary hypotheses are that pembrolizumab plus concurrent chemoradiotherapy is superior to placebo plus concurrent chemoradiotherapy with respect to progression-free survival and overall survival.

High-risk LACC is a population with larger unmet medical need. Approximately half of the women treated with SOC chemoradiotherapy experience a recurrence of their cervical cancer within 2 years. Thus, new treatment modalities and paradigms are needed to significantly improve the prognosis for women diagnosed with high-risk LACC. It is considered that pembrolizumab and CCRT will be more beneficial to the patient via enhancing immunostimulatory activity of pembrolizumab. Pembrolizumab monotherapy demonstrated durable antitumor activity and manageable safety in patients with advanced cervical cancer and received accelerated approval in patients with advanced PD-L1-positive cervical cancer who experienced progression during or after chemotherapy. Preclinical and preliminary clinical observations from other tumor types provide a strong rationale for testing RT and cisplatin as potentiators of immune checkpoint inhibitors.

Study and scientific rationale are further described in Section 2.1.

4.2.1 Rationale for Endpoints

4.2.1.1 Efficacy Endpoints

Progression-free survival and OS are primary endpoints.

This study will use PFS based on RECIST 1.1 criteria as assessed by investigator and histopathologic confirmation of suspected disease progression (in the absence of radiographic disease progression per RECIST 1.1) as the primary endpoint. Locally advanced cervical cancer is a setting where disease progression is highly informed by clinical judgment, including histopathologic confirmation of disease progression with biopsy. PFS by BICR may introduce bias because of informative censoring, which results from having to censor unconfirmed investigator determined progressions. If BICR cannot confirm the locally determined progression, then these cases would be censored at the time of local progression for the BICR analysis of PFS. PFS by investigator is anticipated to result in fewer events censored from PFS analysis compared with BICR and, therefore, to preserve available power for PFS analysis. Investigator is therefore considered a more appropriate primary endpoint in this disease setting. For these reasons, the primary endpoint is PFS by investigator and PFS by BICR is now a secondary endpoint. Progression-free survival is an acceptable measure of clinical benefit for a late stage study that demonstrates superiority of a new antineoplastic therapy, especially if the magnitude of the effect is large and the therapy has an acceptable risk/benefit profile. The use of PFS per RECIST 1.1 is typically considered acceptable by regulatory authorities in a double-blinded randomized controlled study.

Overall survival has been recognized as the gold standard for the demonstration of superiority of a new antineoplastic therapy in randomized clinical studies.

Secondary efficacy endpoints include PFS based on RECIST 1.1 criteria CR at 12 weeks and ORR as assessed by investigator and BICR.

Complete response at 12 weeks and ORR, as assessed by both investigator and BICR per RECIST 1.1 criteria, are commonly accepted endpoints by both regulatory authorities and the

oncology community to assess response and the durability of these responses to oncology treatments.

RECIST 1.1

RECIST 1.1 will be used by the investigator and BICR when assessing images for efficacy measures and by the local site when determining eligibility (Section 8.2.1.5) [NA 2008]. Although traditional RECIST 1.1 references a maximum of 5 target lesions in total and 2 per organ, this protocol has implemented a modification to RECIST 1.1 to allow a maximum of 10 target lesions in total and 5 per organ.

Analyses by PD-L1 Status:

As a secondary endpoint, OS and PFS by PD-L1 status (by CPS) will be compared. Progression-free survival assessment by the investigator will include RECIST 1.1 or histopathologic confirmation of suspected disease progression (in the absence of radiographic disease progression per RECIST 1.1). Cervical cancer is overwhelmingly an HPV-driven cancer, resulting in high levels of PD-L1 expression [Liu, Y., et al 2019]. The baseline PD-L1 scores may increase significantly due to radiotherapy and chemotherapy, since it has been demonstrated that both regimens may increase immunogenicity significantly. Although the CPS score in untreated cases is unknown, we may expect high prevalence given that this is an HPV-driven cancer [Liu, Y., et al 2019]. In addition, PD-L1 status at baseline (all participants), after CRT and at progression (for participants with available biopsies) will be evaluated. The PD-L1 status will be tested in “real-time” and will provide CPS information early in study. This may help deconvolute between different CPS scores and aid in potentially deciding which cutoff may be used for further analyses. Statistical analysis will be performed to assess the efficacy by PD-L1 status.

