Abbreviations: AE=adverse event; aPTT / PTT=activated partial thromboplastin time / partial thromboplastin time; BT=brachytherapy; C=Cycle; CCRT=concurrent chemoradiotherapy; CT=computed tomography; ctDNA=circulating tumor deoxyribonucleic acid; D=day; EBRT=external beam radiotherapy; ECG=electrocardiograph; ECOG=Eastern Cooperative Oncology Group; EQ-5D-5L=EuroQoL 5 Dimension Questionnaire; EORTC QLQ-C30=European Organization for Research & Treatment of Cancer Quality of Life Questionnaire global health status; EORTC QLQ-CX24=European Organization for Research & Treatment of Cancer Quality of Life Questionnaire (Symptom Score for Cervical Cancer); EOT=end of treatment; FDG=fluorodeoxyglucose; FT3=free T3 thyroid hormone; FT4=free thyroxine; HBV=hepatitis B virus; HCV=hepatitis C virus; HIV=human immunodeficiency virus; ID=identity; INR=international normalized ratio; IRT=interactive response technology; IV=intravenous; MRI=magnetic resonance imaging; PET=positron emission tomography; PGI-C=Patient Global Impression of Change; PGI-S=Patient Global Impression of Severity; PRO=patient-reported outcomes; PT=prothrombin time; QW=dosing every week; QW3=dosing every 3 weeks; QW6=dosing every 6 weeks; Q12W=every 12 weeks; Q24W=every 24 weeks; RECIST=Response Evaluation in Solid Tumor; RNA=ribonucleic acid; SAE=serious adverse event; T3=T3 thyroid hormone; TSH=thyroid-stimulating hormone; WOCBP=woman of childbearing potential.

- a. If the Discontinuation Visit occurs \geq 30 days from last dose of study treatment, a separate Safety Follow-up Visit is not required.
- b. Participants who discontinue study intervention for reasons other than RECIST 1.1 radiographic disease progression (including those with histopathologic confirmation of suspected disease progression) will have posttreatment follow-up imaging for disease status until disease progression is documented radiographically per RECIST 1.1 by the investigator, withdrawal of consent, pregnancy, death, or loss to follow-up, whichever comes first.

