8.10.4.2 Efficacy Follow-up Visits

Participants who complete the protocol-required cycles of study intervention or who discontinue study intervention will begin the Efficacy Follow-up Phase and should be assessed every 12 weeks for the first 2 years, every 24 weeks during the third year, and annually thereafter to monitor disease status. Efficacy Follow-up visits should align with the posttreatment imaging visit schedule (see Section 8.2.1.2). For participants who discontinue study intervention for reasons other than radiographic disease progression (including those with histopathologic confirmation of suspected disease progression) will have posttreatment follow-up imaging for disease status until disease progression is documented radiographically per RECIST 1.1 by the investigator, or until withdrawal of consent, pregnancy, death, or loss to follow-up, whichever comes first. Information regarding poststudy anticancer treatment will be collected if new treatment is initiated. Participants who completed all efficacy assessments and/or will not have further efficacy assessments due to documented disease progression per RECIST 1.1 must enter the Survival Follow-up Phase.

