9.4.2 Secondary

PFS BICR: The time from randomization to the first documented disease progression per RECIST 1.1 as assessed by BICR, or death due to any cause, whichever occurs first.

PFS INV at 2 years: The proportion of participants that are PFS event-free at 2 years per RECIST 1.1 as assessed by investigator or by histopathologic confirmation of suspected disease progression (in the absence of radiographic disease progression per RECIST 1.1).

PFS BICR at 2 years: The proportion of participants that are PFS event-free at 2 years per RECIST 1.1 as assessed by BICR.

OS at 3 years: The proportion of participants that are OS event-free at 3 years.

CR rate at 12 weeks after completion of concurrent chemoradiotherapy: The proportion of participants that achieve CR at 12 weeks after CCRT per RECIST 1.1 as assessed by investigator and BICR, respectively.

ORR: The proportion of participants in the analysis population who have an OR, defined as a complete response (CR) or a partial response (PR) per RECIST 1.1 as assessed by investigator and BICR, respectively.

PFS INV by PD-L1: The time from randomization to the first documented disease progression per RECIST 1.1 as assessed by investigator or by histopathologic confirmation of suspected disease progression, by PD-L1 status (by combined positivity score).

[figure not shown]
PFS BICR by PD-L1: The progression-free survival per RECIST 1.1 as assessed by BICR, or death due to any cause, whichever occurs first, by PD-L1 status (by combined positivity score).

OS by PD-L1: The time from randomization to death due to any cause, by PD-L1 status (by combined positivity score).

PFS2: The time from randomization to subsequent disease progression after initiation of new anticancer therapy, or death from any cause, whichever occurs first. If progression after next-line therapy cannot be measured, a PFS2 event is defined as end or discontinuation of next-line treatment or death from any cause, whichever occurs first.

PROs: Endpoints will be assessed by EORTC QLQ-C30 global score and physical function subscale, and EORTC QLQ-CX24 symptoms specific scale. Details will be provided in the sSAP.

Safety and tolerability will be assessed by clinical review of all relevant parameters including adverse events, laboratory values and vital signs.

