9.6.1.3 Progression-free Survival at 2 Years

Progression-free survival at 2 years and 95% CI will be estimated using Kaplan-Meier method. The approach for testing on difference in outcome at a fixed point in time will be used for comparison of the PFS rate at 2 years between 2 treatment groups [Klein, J. P. 2003]. The difference in PFS rate at 2 years, its 95% confidence interval and nominal p-value will be reported.

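### BICR PFS: the stated censoring at an unconfirmed local progression is unnecessary while scanning continues, does not match the endpoint definition, and is likely to overstate the BICR 2-year rate

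*Combined protocol and SAP*

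**What the plan says.** Section 4.2.1.1, explaining why investigator PFS is primary, states that "PFS by BICR may introduce bias because of informative censoring, which results from having to censor unconfirmed investigator determined progressions". It then gives the rule: where BICR does not confirm the local call, "these cases would be censored at the time of local progression for the BICR analysis of PFS".

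Section 9.4.2 defines the secondary endpoint as "The time from randomization to the first documented disease progression per RECIST 1.1 as assessed by BICR, or death due to any cause". Nothing there ends follow-up at an unconfirmed local call. The same section lists the BICR 2-year endpoint, "The proportion of participants that are PFS event-free at 2 years per RECIST 1.1 as assessed by BICR", and BICR PFS by PD-L1 status. Section 9.6.1.3 gives the estimator: "Progression-free survival at 2 years and 95% CI will be estimated using Kaplan-Meier method".

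On follow-up, Section 8.10.4.2 says that participants who stop treatment without radiographic progression, biopsy-confirmed cases included, "will have posttreatment follow-up imaging for disease status until disease progression is documented radiographically per RECIST 1.1 by the investigator". Footnote b of Table 1 says the same. Section 8.2.1.2 requires participants treated beyond progression to continue tumor assessments, with all scans going to the imaging CRO. The synopsis and Section 8.10.4.3 provide survival follow-up for all participants. For participants who discontinue because of radiographic progression, Section 8.2.1.4 makes the discontinuation scan the last one required.

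Table 9 refers the censoring of BICR PFS to Table 7, which is redacted.

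**The concern.** Kaplan-Meier estimation assumes that a censored participant has the same future risk as those who remain under observation. A participant censored because the investigator has just called progression probably has a higher risk. Removing that participant then raises the estimated BICR PFS curve.

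The plan presents this censoring as something it has to do. For two groups it does not. A biopsy-only progression is one in which the investigator saw no RECIST 1.1 progression on imaging. If BICR agrees, there is nothing to confirm on that date, yet scans continue and may later show the event that Section 9.4.2 counts. Participants scanned while treated beyond progression are in the same position. Deaths in both groups are also collected.

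The analyses at stake are BICR PFS, its 2-year rate and its PD-L1 breakdown. They provide a central reading to set beside an investigator-assessed primary endpoint, so a reader needs to know which events they include.

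**Working it through.** **The plan's own figure.** The documents give no figure for BICR PFS. The primary PFS design can be reproduced: with 304 events, HR 0.660 and one-sided alpha 0.025, power = Φ(√304/2 × |ln 0.660| − 1.96) = Φ(8.718 × 0.4155 − 1.96) = Φ(1.66) = 95.2%, against the stated 95%. That test uses investigator PFS and does not depend on the BICR rule.

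**Inputs for the BICR rate.**
- Investigator 2-year PFS, S: 62.1% (the external control-arm rate quoted in Section 2.2.3), or 50% (from the statement in Section 4.2 that about half recur within 2 years).
- Share of local events not confirmed by BICR, u: not given; assumed 10%, 20% or 30%.
- Median time from an unconfirmed local progression to BICR progression or death: not given; assumed 3, 6, 12 or 24 months.

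**Model.** Local events have constant hazard L = −ln(S)/24 per month. After an unconfirmed local event, the BICR event has hazard m = ln 2/median.
- Censoring at local progression: KM(24) = S^(1−u).
- Endpoint as defined in Section 9.4.2: S + uL × [exp(−24m) − exp(−24L)]/(L − m).

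**Worked case:** S = 0.621, u = 0.20, median 6 months. L = 0.4764/24 = 0.01985 and m = 0.1155.
- Censored: 0.621^0.8 = 68.3%.
- As defined: 0.621 + 0.2 × 0.01985 × (0.0625 − 0.621)/(0.01985 − 0.1155) = 0.621 + 0.023 = 64.4%.
- Overstatement: 3.9 points. A simulation of 400,000 participants gave 68.3% and 64.4%.

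**Overstatement of the 2-year rate, in points:**

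| S | u | Censored rate | 3 mo | 6 mo | 12 mo | 24 mo |
|---|---|---|---|---|---|---|
| 62.1% | 10% | 65.1% | 2.5 | 1.9 | 1.1 | 0.4 |
| 62.1% | 20% | 68.3% | 5.0 | 3.9 | 2.3 | 0.9 |
| 62.1% | 30% | 71.6% | 7.8 | 6.1 | 3.7 | 1.6 |
| 50% | 10% | 53.6% | 2.9 | 2.1 | 1.1 | 0.1 |
| 50% | 20% | 57.4% | 6.0 | 4.5 | 2.4 | 0.5 |
| 50% | 30% | 61.6% | 9.4 | 7.2 | 4.1 | 1.2 |

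The short-lag columns presume that scanning continues. Where it has stopped, only deaths can be counted, and the longer-lag columns are the better guide.

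**When the bias vanishes.** The two formulas agree when m = L(1 − u). For S = 62.1% and u = 20% that is a median of ln 2/(0.01985 × 0.8) = about 44 months. Shorter medians give an overstatement.

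**Between-arm difference at 2 years.** Control is 62.1%, pembrolizumab is 0.621^0.66 = 73.0%, and the median lag is 6 months:

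| Unconfirmed, control / pembrolizumab | As defined | Censored |
|---|---|---|
| 20% / 20% | 10.3 points | 9.5 points |
| 30% / 20% | 9.2 points | 6.1 points |
| 20% / 30% | 11.2 points | 11.9 points |

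The direction depends on how non-confirmation is split between the arms, and the documents do not give that.

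**The case against.** The strongest reply is that the binding rule cannot be seen. Section 4.2.1.1 is a rationale section written in the conditional, Table 7 holds the actual rules, and part of Section 9.6.1.1 is not shown. It is normal to pair an endpoint definition with a separate censoring table. A reader might infer that every participant with an unconfirmed local progression is censored in the analysis, but the visible text cannot establish that. What remains is that the visible rule and the visible definition treat the same later events differently, and nothing visible reconciles them.

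A reader might also infer that later RECIST progressions are generally discarded. The imaging rules do not support this. After an investigator-called radiographic progression, scanning normally stops, so for that group later progressions are mostly never observed and the uncounted events are mainly deaths. For the same reason, no specific loss of BICR events or power can be derived: such a figure would presume scanning that the protocol does not require, and the share of biopsy-only cases is not given.

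Nor would it be safe to count later deaths in the imaging-stopped group while censoring its survivors at their last scan. Who stays at risk would then depend on who later dies, which is itself informative censoring.

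Finally, BICR reads independently and may see progression on scans that the investigator called negative, so not every biopsy-only case will be unconfirmed. The sponsor also discloses the bias, made BICR PFS secondary, and under Section 9.6.1 reports only nominal p-values outside the error-controlled tests. All of this limits the consequences. Disclosure does not, however, explain why participants still being scanned need to be censored.

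**Conclusion.** The point holds for participants whose imaging continues after an unconfirmed local progression: biopsy-only progressors and those scanned while treated beyond progression. For them the stated censoring is avoidable, departs from Section 9.4.2, and is likely to overstate BICR 2-year PFS.

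The size is undetermined. Across the assumed ranges it runs from 0.1 to 9.4 points, with the lower part of the range more relevant where only deaths remain observable. This rests on constant hazards and on assumed values for the non-confirmation share and the lag. The upward direction requires that participants with an unconfirmed progression have a higher later event rate than those still at risk, which is likely but not shown in the documents.

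The effect on the 2-year difference or the hazard ratio can go either way. Primary PFS, OS and the alpha plan are unaffected. This is an inexpensive correction to secondary analyses, and Table 7 may already contain it.

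**What to change.** Reconcile Section 4.2.1.1, Section 9.4.2 and the BICR rules in Table 7, so that all three state:

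1. A local progression that is histopathologic only, or otherwise unconfirmed by BICR, is not itself a censoring event while BICR-read imaging continues. Later BICR-read progressions, and deaths during that continued imaging, count as events.
2. Where imaging stopped at local radiographic progression, censoring at that point stays in the main BICR analysis.
3. Two sensitivity analyses cover that group: one counts later deaths, with survivors carried to the last date known alive so that remaining at risk does not depend on a future death; the other treats the unconfirmed local progression as an event.

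Report the number of unconfirmed local progressions by arm, split into biopsy-only and radiographic, since the direction of any bias in the comparison depends on it.

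The cost is a few sentences and one or two extra runs. No added scans are needed, because the main-analysis change applies only to participants already being imaged. The downside is that some counted events may follow new anticancer therapy or a gap in scans, so the text should say how this rule works with any Table 7 rule on those situations.
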